## 16 ASSESSMENT OF SAFETY

### 16.1 Specification Of Safety Parameters

The descriptions and grading scales found in the revised Common Terminology Criteria for Adverse Events (CTCAE) version 5.0 will be utilized for AE reporting and toxicity assessment.

#### 16.1.1 Definition Of Adverse Events (AE)

##### **Adverse Event**

An adverse event is any untoward medical occurrence associated with the use of a drug in humans, whether or not considered drug related.

An adverse event can be any unfavorable and unintended sign, symptom, or disease temporally associated with the use of a drug and does not imply any judgment about causality. An adverse event can arise with any use of the and with any route of administration, formulation, or dose, including an overdose.

##### **Expectedness**

An adverse event “unexpected” if it is not listed in the investigator brochure or is not listed at the specificity or severity that has been observed; or, if an investigator brochure is not required or available, is not consistent with the risk information described in the general investigational plan or elsewhere in the current application. “Unexpected,” as used in this definition, also refers to adverse events that are mentioned in the investigator brochure as occurring with a class of drugs or as anticipated from the pharmacological properties of the drug but are not specifically mentioned as occurring with the Particular drug under investigation.

Events not listed in the investigator brochure are considered “unexpected” and those listed are considered “expected.”

##### **Serious**

An adverse event or is considered “serious” if, in the view of either the investigator or sponsor, it results in any of the following outcomes:

- Death
- Life-threatening adverse event
- Inpatient hospitalization or prolongation of existing hospitalization
- A persistent or significant incapacity or substantial disruption of the ability to conduct normal life functions
- A congenital anomaly/birth defect

Important medical events that may not result in death, be life-threatening, or require hospitalization may be considered serious when, based upon appropriate medical judgment, they may jeopardize the patient or patient and may require medical or surgical intervention to prevent one of the outcomes listed in this definition.

### **Life-threatening**

An adverse event is considered “life-threatening” if, in the view of either the investigator or sponsor, its occurrence places the participant at immediate risk of death. It does not include an adverse event or suspected adverse reaction that, had it occurred in a more severe form, might have caused death.

#### **16.1.2 Relationship To Study Agent**

The relationship to study intervention or study participation must be assessed and documented for all adverse events. Evaluation of relatedness must consider etiologies such as natural history of the underlying disease, concurrent illness, concomitant therapy, study-related procedures, accidents, and other external factors.

### **Attribution**

AEs will be assessed as Unrelated, Possibly Related, Probably Related, or Definitely Related. Possible, Probably, or Related AEs will all be considered Related for this protocol. This is the relationship between an adverse event or serious adverse event and the study treatment.

Attribution will be assigned as follows:

Attribution	Definition
Unrelated	There is no reasonable possibility that there is a causal relationship between the study treatment and the AE.
Related	The AE is possibly related to the study treatment.

#### **16.2 Reporting Procedures**

##### **16.2.1 ADVERSE EVENT REPORTING**

Information for adverse events, whether reported by the participant, directly observed, or detected by physical examination, laboratory test or other means, will be collected, recorded, followed and reported in the study Case Report Form (CRF) as described in the following sections.

ALL adverse events experienced by participants will be monitored/collected/reported as follows:

- Adverse events will be monitored/collected/reported from the start of study treatment, throughout the study, and up to and including day 30 after the last dose of study drug or until the 30 day safety follow up.
- Adverse Events of Special Interest (AESI): Development of new bacterial or fungal infection in this study is an AESI, and should be reported regardless of severity or seriousness. Reporting should

be completed using the protocol specific AESI Reporting Form and FDA 3500 A MedWatch form and all supporting documents to both KUCC Regulatory department: [[contact]](mailto:[contact]) and [[contact]](mailto:[contact]) (or by fax to [contact]). AESI should also be entered in CRIS (Velos) system

- SERIOUS adverse events that meet the definition(s) of a serious adverse event will be monitored/collected/reported from start of study treatment, throughout the study, and up to and including day 30 after the last dose of study drug or until the 30 day safety follow up.

Participants who experience an ongoing adverse event related to a study procedure and/or study medication beyond 30 days will continue to be contacted by a member of the study team until the event is resolved, stabilized, or determined to be irreversible by the Sponsor-investigator.

Study participants should also be instructed to report any new serious post-study event(s) that might reasonably be related to participation in this study.

Medical conditions/diseases present before starting study treatment are considered adverse events only if they worsen after initiation of study drug.

Abnormal laboratory values or test results constitute adverse events only if they induce clinical signs or symptoms or require therapy. In this case they will be recorded on the Adverse Events CRF, along with the associated signs, symptoms or diagnosis.

All SAEs recorded throughout this study will be continued to be monitored until resolution or stabilization.

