##### 3.2.2 Secondary Endpoints

What is being measured	Measurement time frame	Measurement Tool
Change in 7 point-ordinal scale	Baseline, Day 3, Day 7, Day 14, Day 28 and follow-up.	Using WHO COVID-19 Ordinal scale measuring: Proportion and time to patients with greater than 2 point improvement on the 7 point categorical scale

Change in oxygen saturation-normalization	Baseline and continuous throughout hospitalization	Peripheral capillary pulse oximeter to measure: SpO 2 /FiO 2 ratio over time, sustainment of normalization in 24 hours, and relative shifts in SpO 2 /FiO 2 categories (<235, between 235 and 315, greater than 315) over time
Need for advanced respiratory care	Baseline and continuous throughout hospitalization	Derived from medical record: time of intubation in the ICU, duration of ICU care in days, duration of overall hospitalization in days
All-cause mortality	Baseline and through d60	Noted in patient medical record
Number and percent of adverse events (AEs) and serious adverse events (SAEs); mean change from baseline lab values, vital signs, and ECG	Baseline through day 14 or at discharge <d14, at d28 ±3, d45 ±3 and d60 ±3 (lab values will be examined up to d45) 	CTCAE v5.0; changes in CBC, CMP, Mg, PT/INR, PTT, GGT, hsCRP, D-dimer, LDH, ferritin, creatine kinase, troponin-i, procalcitonin; standard vital signs measurement with pulse ox; ECG
Proportion of participants with normalization of fever for 24h	Baseline through day 14 or at discharge <d14	Standard daily vital measurement and obtained from patient medical record
Development of new bacterial or fungal infection (AE of Special Interest)	Continuous throughout hospitalization	Noted in patient medical record
Incidence of ARDS  through day 14 or at discharge <d14	From day 1 though day 14 or at discharge <d14	Noted in patient medical record
Change in plasma cytokines IL-1β, IL-6, IL-8 and TNF-α	Baseline, day 3, day 7 (or discharge <d7), day 14 (or discharge >d7 and <d14)	Plasma collected from blood and assayed on Luminex panel performed by KUMC BBV Core

 For clarification, lab values will be collected at baseline, day 3, day 7 (or discharge <d7), day 14 (or discharge >d7 and <d14), at day 28 ±3, day 45 ±3. Vital signs, pulse ox will be collected baseline through day 14 or at discharge <d14, at d28 ±3, d45 ±3 and d60 ±3 (lab values will be examined up to d45)

 ARDS Criteria:

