### 4.3 End of Study Definition

Completion of single cycle of treatment with 14 day follow or stopped due to participant factor or physician discretion.

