#### Safety Follow up

- **Day 45 Post Hospital Day 1 ( $\pm 3$  days)**
  - Vitals
  - Prior and concomitant medications
  - Follow-up adverse event status
  - Survival Status
  - Pregnancy status
  - CBC with differential
  - PT, INR
  - PTT
  - CMP
  - Mg
  - GGT
  - Creatine kinase
  - Troponin I
- **Day 60 Post Hospital Day 1 ( $\pm 3$  days)**
  - Phone call to follow up adverse event status
  - Survival Status

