### 12.1 Adverse Event Monitoring

Medical history adverse events are recorded and graded using Common Terminology Criteria for Adverse Events (CTCAE) version 5.0. Serious adverse event and adverse event monitoring begins after initiation of study treatment and continues until the Day 60 safety follow-up. This Day 60 follow-up check and will be done by phone.

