### 12.2 Adverse Event Reporting

Information for adverse events, whether reported by the participant, directly observed or detected by physical examination, laboratory test or other means, will be collected, recorded, followed and reported in the CRIS system within 5 days of being reported.

All adverse events experienced by participants will be collected. Medical conditions are collected as baseline adverse events and evaluated as above. Additional adverse event monitoring begins after initiation of study treatment and continues until the 60 day safety follow up.

Participants who experience an ongoing adverse event related to a study procedure and/or study medication beyond the 60 day safety follow up will continue to be contacted by a member of the study team until the event is resolved, stabilized, or determined to be irreversible by the Sponsor/Investigator.

Study participants should also be instructed to report any new serious post-study event(s) that might reasonably be related to participation in this study.

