#### **Safety Summaries**

The FAS population will be used for the analysis of safety data (AEs, exposure to study medication, clinical laboratory values, vital signs, and ECG).

AEs will be coded with the Medical Dictionary for Regulatory Activities. Treatment-emergent adverse events (TEAEs) are defined as AEs with an onset date on or after the date of first administration of study medication and before the date of last administration of study medication + 30 days. TEAEs will be presented by system organ class and preferred term in frequency tables. Patients with multiple AEs will be counted only once within each preferred term and system organ class. Key patient information for patients with an AE with an outcome of death, patients with SAEs, and patients with an AE leading to discontinuation of study medication will be listed.

Laboratory data (hematology, serum chemistry, coagulation, and urinalysis) will be converted to Système International units for reporting and processing purposes. Absolute values and changes from baseline will be presented descriptively. Laboratory data outside study specific reference ranges will be listed. Vital signs and ECG parameters will be presented descriptively.

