### Adverse Event Monitoring

Medical history adverse events are recorded and graded using Common Terminology Criteria for Adverse Events (CTCAE) version 5.0. Serious adverse event and adverse event monitoring begins after initiation of study treatment and continues until the Day 60 safety follow up.

Adverse event data collection and reporting are a part of every clinical trial and are done to ensure the safety of participants enrolled in the studies as well as those who will enroll in future studies using similar agents.

Adverse events should be evaluated to determine

- Start and end dates
- Severity or grade
- Seriousness
- Relationship to study agent
- Action taken (i.e., dose held, dose reduced, medical intervention)
- Outcome (i.e., resolved without sequelae, resolved with sequelae, ongoing)

Participants experiencing an adverse event, regardless of its relationship to study drug will be monitored until:

- Adverse event resolves or the symptoms or signs that constitute the adverse event return to baseline.
- Clinically significant abnormal laboratory values have returned to baseline.
- The treating investigator has determined there is a satisfactory explanation other than the study drug for the changes observed.
- Death

The following laboratory abnormalities should be documented and reported as adverse events.

- Meets the definition of an SAE.
- Requires medical intervention (i.e., dose modification and/or other intervention such as supportive medication administration, supplementation, physical therapy, diet change, fluid administration, transfusion, additional testing, etc.)

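### Protocol 16.2.1 ends adverse event collection 30 days after the last dose, while the rest of the protocol carries it to Day 60

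*Protocol*

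**What the plan says.** **To Day 60.** Section 12.1: "Serious adverse event and adverse event monitoring begins after initiation of study treatment and continues until the Day 60 safety follow-up". Section 12.2: "Additional adverse event monitoring begins after initiation of study treatment and continues until the 60 day safety follow up". Appendix A, under Adverse Event Monitoring, says that it "continues until the Day 60 safety follow up". The safety endpoint in 3.2.2 has the time frame "Baseline through day 14 or at discharge <d14, at d28 ±3, d45 ±3 and d60 ±3". In section 10.1.2 the Day 60 contact is listed as "Phone call to follow up adverse event status", and the AE row of the schedule in 10.4 is marked at Days 28, 45 and 60.

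**To 30 days after last dose.** Section 16.2.1 ends collection "up to and including day 30 after the last dose of study drug or until the 30 day safety follow up". It says this twice, once for all AEs and once for SAEs. The same sentences also say that collection runs through the whole study. For ongoing related events, 16.2.1 continues contact past 30 days, where 12.2 continues it past the 60-day follow-up.

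**Analysis window.** Section 15.3 and the Protocol Summary define a treatment-emergent AE (TEAE) as one with onset on or after the first dose and "before the date of last administration of study medication + 30 days". The SAP text gives no TEAE definition and no AE window. It refers to attached DSMB table shells.

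**Last dose.** Study drug is given for up to 14 days and stops at discharge or new mechanical ventilation (Protocol Summary; sections 9 and 11.4).

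**The concern.** Two sections that each read as the governing rule give different end dates for the same data. Section 16.2.1 is the one headed for AE reporting, so a site could reasonably work from it, and it points to a follow-up visit that does not exist. An SAE on Day 50, for example, must be captured under 12.1 but falls outside the period named in 16.2.1.

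Such events matter for more than the final tables. Treatment-related SAE counts feed the DSMB's two-weekly rate review (18.2), and attributable events of grade 3 or higher feed the 10% trigger for full review (15.7). In a trial of about 20 patients, one or two events can decide whether such a threshold is met.

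A second, smaller issue concerns analysis. The TEAE window is counted from the last dose, and the last dose depends on how the patient does. The documents available here name no display of the non-serious AEs that occur between the TEAE cut-off and Day 60.

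**Working it through.** The plan states no figure to reproduce. The check is calendar arithmetic.

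**Inputs**
- Hospital Day 1 is the first dosing day; last dose on day L, from 1 to 14 (section 9; daily procedures in 10.1.1).
- Section 16.2.1 includes day 30 after the last dose, so collection ends on Day L + 30.
- The TEAE rule says before last dose + 30 days, so its last included day is L + 29.
- Sections 12.1 and 12.2, Appendix A and 3.2.2 end at Day 60, with a visit window of ±3 days.

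**Results**

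| Last dose (L) | 16.2.1 ends, L + 30 | Days short of Day 60, 60 − (L + 30) | Last TEAE day, L + 29 |
|---|---|---|---|
| Day 1 | Day 31 | 29 | Day 30 |
| Day 7 | Day 37 | 23 | Day 36 |
| Day 14 | Day 44 | 16 | Day 43 |

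- Spread between patients: 44 − 31 = 13 days.
- With the Day 60 contact made between Day 57 and Day 63, the shortfall runs from 57 − 44 = 13 days to 63 − 31 = 32 days.
- The latest closing day, Day 44, comes before Day 45. On nominal dates, both the Day 45 and the Day 60 contacts fall after the 16.2.1 window has closed, for every patient.
- The two last-dose rules differ by one day: an event exactly 30 days after the last dose is collected under 16.2.1 but is not a TEAE.

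**Does the whole-study wording in 16.2.1 settle the matter?** Not clearly. The sentence goes on to name an earlier end point. The protocol is also unclear about how long the study lasts: section 10.4.2 speaks of a 60-day study period, while 4.3 defines the end of study as "Completion of single cycle of treatment with 14 day follow". If that means 14 days after a last dose on Day 14, it ends on Day 14 + 14 = Day 28. The wording makes 16.2.1 ambiguous and does not bring it into line with Day 60.

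**The case against.** The strongest reply is that a site would have to overlook much of the protocol to miss a late event.
- Follow-up visits are counted from Hospital Day 1, not from the last dose. Section 10.2 says that stopping treatment does not remove the need for follow-up, and 11.4 continues safety monitoring on the study schedule.
- Sections 16.2.2 and 16.2.3 require entry of all AEs and SAEs whatever their cause, with no cut-off day, and 16.2.1 itself asks participants to report later serious events that might be related.
- Deaths are captured to Day 60 as all-cause mortality, and the death and SAE listings in 15.3 are not worded as limited to TEAEs.

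All of this stands. It makes loss of events less likely, but it does not say which end date applies. The entry rules in 16.2.2 and 16.2.3 state what must be recorded and how fast, not how long a site must keep asking.

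A reader might also infer that a TEAE window shorter than the collection period is an error. It is not; that arrangement is conventional. The half-life of about 9 to 11 hours (section 1.1.4.4) makes 30 days a generous margin: 720 hours ÷ 11 hours is about 65 half-lives.

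A reader might go further and infer that late events are lost unevenly, so that AE proportions cannot be compared between arms. The documents do not support this. Windows differ between patients, by up to 13 days, but a difference between arms would need last-dose timing to differ by arm. That could happen if the drug changes discharge or ventilation, which is its aim (section 1.2), but it cannot be known from the plan. The SAP also plans no formal hypothesis test.

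**Conclusion.** The contradiction is real and should be reconciled. One section ends AE and SAE collection on Day 31 to Day 44; the other sections and the schedule run to Day 60. The disputed period is 16 to 29 days per patient, and 16.2.1 refers to a visit that is not scheduled.

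The consequence is a risk. Whether any event goes unreported depends on which section a site follows, and most of the protocol points to Day 60. Bias between arms is not shown. What is certain is narrower: under the current TEAE rule, events after Day 30 to Day 43 stay out of the TEAE tables even if collected, and the documents available here give no other table for the non-serious ones.

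This rests on dosing starting on Hospital Day 1, a last dose between Days 1 and 14, and the last contact on study Day 60. If that contact is counted as 60 days after Hospital Day 1, each shortfall grows by one day. The SAP's attached shells are not available, so an AE window may be defined there.

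**What to change.** 1. In 16.2.1, change both the AE and the SAE bullet to collection from the first dose through the Day 60 contact, and delete the 30-day safety visit.
2. In the same section, change the sentence on ongoing related events so that its threshold is the Day 60 contact, as in 12.2.
3. Keep the TEAE definition in 15.3 and the Protocol Summary. Add to 15.3 and the SAP a supplementary table or listing, by arm, of all AEs collected from Day 1 to Day 60. Replacing the TEAE table as the main display would be a matter of preference and is not needed.
4. While editing, bring the end-of-study definition in 4.3 into line with the 60-day follow-up.

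No new visit is needed: the Day 45 visit and the Day 60 call already exist. The cost is a wording change in the protocol, one added display in 15.3 and the SAP (and possibly its shells), and a few more late, probably unrelated events to record.

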### 11.4 Participant Discontinuation/Withdrawal from the Study

- Duration of therapy will depend on individual response, evidence of disease progression and tolerance. Any one of the listed items below will be defined as a stopping criteria event. Participants will be removed from protocol therapy for any of the unacceptable adverse event listed below. Participants will have study treatment withdrawn but will remain in the study for follow-up, if any of the following occur:
  - Intubation and ventilation
  - Intercurrent illness that prevents further administration of treatment.
  - Unacceptable adverse event(s) defined as:
    - Malignancy (except for non-melanoma skin cancers)
    - Hepatitis B re-activation
    - Rhabdomyolysis
    - Demyelinating disease
    - Heart failure
    - Lupus-like syndrome

- Hypersensitivity reaction
- Gastrointestinal perforation
- WBC  $<1 \times 10^3/\mu\text{l}$
- ANC  $<0.5 \times 10^3/\mu\text{l}$
- Platelet count  $<50 \times 10^3/\mu\text{l}$
- Hemoglobin:  $<6.5 \text{ g/dl}$
- AST, ALT:
  - $>5 \times \text{ULN}$
  - $>3 \times \text{ULN}$  and (total bilirubin  $>2 \times \text{ULN}$  or international normalized ratio [INR]  $>1.5$ )
  - $>3 \times \text{ULN}$  with appearance of fatigue, nausea, vomiting, right upper quadrant pain or tenderness, fever, rash and/or eosinophilia ( $>5\%$ )
- Serum creatinine:  $>2 \times \text{ULN}$
- Serious bacterial or fungal infection
- Other major developing illness or conditions at the discretion of the treating physician
- Participant demonstrates an inability or unwillingness to comply with the oral medication regimen and/or documentation requirements
- Participant decides to withdraw from the protocol therapy
- General or specific changes in the participant's condition render the participant unacceptable for further treatment in the judgment of the treating investigator
- Major violation of the study protocol (i.e., unable to adhere to study schedule) that in the opinion of the treating investigator, puts the participant at undue risk
- Discontinuation of the study by KUMC
- Confirmed pregnancy
- Completed Overall Survival (OS) follow up as per protocol
- Lost to follow-up
- Death

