#### 15.7 Study Stopping Rules

If 10% or more of the patients evaluated cumulatively every two weeks demonstrate any adverse event of grade 3 or higher that is attributable to the investigational agent and that is not alleviated or controlled by appropriate care or antibiotic therapy within 14 days, will trigger a full review by the data safety

monitoring committee to determine the appropriate course of action. The DSMB may request suspension of the study to allow time for a full committee review or may permit the study to continue after formal review. The DSMB can, however, request a full review at any time in response to an unexpected toxicity regardless of whether the 10% threshold is met.

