#### Serious Adverse Event (SAE) Definition

A Serious Adverse Event (SAE) is any untoward medical occurrence that at any dose:

- Results in death.
- Is life-threatening (defined as an event in which the participant was at risk of death at the time of the event; it does not refer to an event which hypothetically might have caused death if it were more severe).
- Requires inpatient hospitalization or causes prolongation of existing hospitalization.
- Results in persistent or significant disability/incapacity.
- Is a congenital anomaly/birth defect
- Is an important medical event defined as a medical event or multiple medical events that may not be immediately life-threatening or result in death or hospitalization but, based upon appropriate medical and scientific judgement may jeopardize the participant or may require intervention (e.g., medical, surgical) to prevent one of the other serious outcomes listed above.
- Suspected transmission of an infectious agent (e.g., pathogenic or nonpathogenic) via the study drug.

Although pregnancy and potential drug-induced liver injury are not always serious by regulatory definition, for the purposes of this protocol, these events are considered to be an SAE and follow the SAE reporting timeline.

Any component of the study endpoints that is considered related to study therapy should be reported as an SAE (e.g., death is an endpoint, if death occurred due to anaphylaxis, anaphylaxis is reported an SAE.)

NOTE: The following hospitalizations are not considered SAE's:

- An Emergency room or other hospital department visit <24 hours that does not result in admission. Unless considered an important medical or life-threatening event)
- Elective surgery planned prior to signing consent.
- Admissions as per protocol for a planned medical/surgical procedure.
- Routine health assessment requiring admission for baseline/trending of health status. (e.g., routine colonoscopy)

- Medical /surgical admission other than to remedy ill health and planned prior to entry into the study. Appropriate documentation is required in these cases.
- Admission encountered for another life circumstance that carries no bearing on health status and requires no medical/surgical intervention. (e.g., lack of housing, economic inadequacy, caregiver respite, family circumstances, administrative reason)

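### Four protocol passages disagree on when a laboratory value is an adverse event, so a laboratory stop under 11.4 can drop out of the AE outputs and the 15.7 count

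*Protocol*

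**What the plan says.** Protocol 11.4 says "Participants will be removed from protocol therapy for any of the unacceptable adverse event listed below". Under the item "Unacceptable adverse event(s) defined as" it mixes diagnoses with plain laboratory limits for WBC, ANC, platelets, hemoglobin, AST/ALT and creatinine. Only one AST/ALT limb adds a clinical condition; its alternatives include "right upper quadrant pain or tenderness, fever, rash and/or eosinophilia". The other limits stand on the number alone.

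Protocol 16.2.1 is restrictive: "Abnormal laboratory values or test results constitute adverse events only if they induce clinical signs or symptoms or require therapy".

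Protocol 16.2.2 is broader. It requires entry in Velos of laboratory findings that are clinically significant, and of anything the investigator considers significant. It then glosses significance, for laboratory tests, as needing medical intervention.

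Appendix A is broader again. Its AE definition gives an abnormal laboratory finding as an example of a sign that can be an AE. Under Adverse Event Monitoring it says "The following laboratory abnormalities should be documented and reported as adverse events", and the criteria are meeting the SAE definition or needing intervention, with dose modification and additional testing among the examples. Its SAE section says that pregnancy and "potential drug-induced liver injury are not always serious by regulatory definition", but are handled as SAEs in this protocol.

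The cumulative DSMB trigger in 15.7 is worded in terms of adverse events: "If 10% or more of the patients evaluated cumulatively every two weeks demonstrate any adverse event of grade 3 or higher". The event must also be attributable to the drug and not controlled by appropriate care within 14 days.

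**The concern.** The same finding can be an AE in one section and not in another. A patient whose platelets or ALT cross an 11.4 limit, without symptoms and without treatment for it, leaves study drug for what 11.4 calls an adverse event. Under 16.2.1 that patient has no adverse event.

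The case is plausible for this drug. Protocol 1.1.4.4 reports a downward trend in ANC in Phase 1 with no clinical consequence, and 1.3.1 lists acute neutropenia as an immediate risk. No Phase 1 subject fell below 500 cells/µL, which is the 11.4 ANC limit, but those were healthy volunteers.

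At stake is whether sites record the same event in the same way. Outputs that start from the AE record inherit the difference, and in a trial this small one record can matter.

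**Working it through.** The plan states no figure to reproduce. The check is textual, followed by a short calculation on 15.7.

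**Step 1. One case under each rule.** Take a value past a bare 11.4 limit, with no symptoms and no therapy.

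| Place in the protocol | Is it an AE? |
|---|---|
| 11.4 | Yes, and treatment stops |
| 16.2.1 | No |
| 16.2.2 | Probably, if the investigator judges it significant; the gloss on intervention leaves room for no |
| Appendix A, AE definition | It can be |
| Appendix A, Adverse Event Monitoring | Yes if it needs dose modification or extra testing; whether a permanent stop counts is not said, and 11.2 does not permit dose modification |
| Appendix A, SAE definition (liver values only) | An SAE if it is potential drug-induced liver injury, a term not tied to the 11.4 AST/ALT limits |

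No passage ranks these rules.

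**Step 2. What depends on the AE record.** The 15.7 count, the treatment-emergent AE tables and the listing of AEs leading to discontinuation (protocol 15.3) all do. The SAP's Safety Summaries section describes only AE tables and refers to attached shells, which are not in the text and may hold more.

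**Step 3. What does not depend on it.** Section 9.1.3 sends each grade 3 or higher toxicity to the DSMB within 24 hours and does not require AE status. Protocol 15.3 lists out-of-range laboratory data. Section 11.4 requires the reason for and date of removal in the eCRF.

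**Step 4. The 15.7 threshold.** The smallest triggering count among n evaluated patients is r = ceil(0.10 × n). The n values are 20 (Protocol Summary; SAP) and 36 (protocol 15.1), plus 10 as an early look.

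- n = 10: r = 1. With one case omitted, 0/10 = 0%: no trigger.
- n = 20: r = 2 (10.0%). With one omitted, 1/20 = 5.0%: no trigger.
- n = 36: r = 4 (4/36 = 11.1%). With one omitted, 3/36 = 8.3%: no trigger.

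**Step 5. Illustration with assumed rates.** Let p be the chance that a patient has an event meeting all the 15.7 conditions, and f the share of such patients whose event is laboratory-only and unrecorded. Neither is in the documents. At full enrolment the chance of reaching the threshold is P(X ≥ r), with X binomial(n, p(1 − f)). For n = 20, p = 0.10, f = 0: 1 − 0.9^20 − 20 × 0.1 × 0.9^19 = 1 − 0.122 − 0.270 = 0.608.

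| n (r) | p | f = 0 | f = 25% | f = 50% |
|---|---|---|---|---|
| 20 (2) | 5% | 0.264 | 0.172 | 0.088 |
| 20 (2) | 10% | 0.608 | 0.449 | 0.264 |
| 20 (2) | 20% | 0.931 | 0.824 | 0.608 |
| 36 (4) | 5% | 0.104 | 0.045 | 0.012 |
| 36 (4) | 10% | 0.491 | 0.283 | 0.104 |
| 36 (4) | 20% | 0.948 | 0.809 | 0.491 |

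This treats 15.7 as a single look, although it is applied every two weeks. It shows the direction and rough size only.

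**The case against.** A reader might infer that these removals bypass the DSMB. The documents do not support that. Section 9.1.3 is worded by toxicity, so 16.2.1 does not switch it off. A liver case classed as potential drug-induced injury is an SAE, and under 16.2.3 an SAE entry in Velos emails the DSMB automatically. Section 15.7 lets the DSMB ask for a full review whether or not 10% is reached, and section 18 has it monitoring every treated participant.

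It can also be said that 16.2.1 is the outlier. Section 11.4 itself calls these values adverse events, 16.2.2 contains no exclusionary wording, and section 12 points readers to Appendix A. Most sites would find it hard to call a value that ends treatment insignificant.

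Finally, 15.7 needs grade, attribution and 14 days without control. A value that needed therapy would already be an AE under 16.2.1, so the omitted group is confined to values that persist without symptoms and without therapy.

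All of this stands as a limit on the consequence, but it does not remove the conflict. Section 9.1.3 concerns whether one patient should continue, and nothing says that it feeds the 15.7 count or the AE tables. The 11.4 limits are not mapped to CTCAE grades, so it cannot be shown that every laboratory removal reaches 9.1.3; one below grade 3 would not count under 15.7 either, but could still be missing from the AE outputs. The section titled for AE reporting is the one with the restrictive wording.

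**Conclusion.** The rules conflict and should be reconciled. The exposure is confined to three places: the treatment-emergent AE tables, the listing of AEs leading to discontinuation, and the 15.7 cumulative count. For the first two it needs only a site that follows 16.2.1 and a removal with no symptoms and no therapy. For the third, the event must also meet every 15.7 condition; then one omission at the threshold (2 of 20, or 4 of 36) is enough to stop the trigger.

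Two stronger readings do not hold. Not every 11.4 laboratory removal would count under 15.7 even if recorded. Nor is laboratory safety hidden as a whole, because protocol 15.3 provides listings of out-of-range values and descriptive summaries of laboratory data. How many patients would be affected cannot be estimated from the documents; the probabilities above rest on assumed rates.

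**What to change.** Reconcile 11.4, 16.2.1, 16.2.2 and Appendix A (Adverse Event Monitoring) on one recording rule. In 16.2.1, add text to this effect: any laboratory value that meets a stopping criterion in 11.4 is recorded as an adverse event with its CTCAE grade, whether or not it causes symptoms or needs therapy, and is assessed against the conditions in 15.7; potential drug-induced liver injury is reported as an SAE, as Appendix A already provides. Align 16.2.2 and Appendix A with it.

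This is a recording rule. It leaves the 11.4 thresholds and the stopping rules as they are. It costs a few sentences and a few extra AE entries, since the values are already collected. Removals that have already happened can be found from the reason for removal in the eCRF and checked for a matching AE record before the tables are produced.
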